# Study Protocol

## INTRODUCTION

Progress in perinatal care results in the increase of preterm infants survivability. Preterm infants need basic life functions support with nutrition being one of these functions. Prematurely born infants often require gastric tube feeding. Transition from enteral (gastric tube) to oral feeding poses a problem for premature infants with cardiovascular and respiratory stability. Therefore, the transition is conducted gradually, taking into account, i.a. the stability of life functions, the maturation of orofacial area reflexes and the efficiency of articulation apparatus, suction-breathing-swallowing coordination, development of autoregulatory mechanisms which are associated with the ability to maintain the activity level which enables feeding. The 32-34 weeks postmenstrual age is usually the moment when premature infants are most likely to begin oral feeding, usually bottle-feeding (the maternal milk, milk from a milk bank, or modified milk). Later on, most premature infants achieve sufficient level of ability to initiate breast or mixed feeding. Indication of proper and effective operations that are aimed at improving the quality and safety of oral feeding is a challenging issue.

One of significant aspects which may contribute to improvement of quality and safety of oral feeding of premature infants is the optimal feeding position. Feeding positioning applied in prematurely born children includes semielevated (SEP) and side-lying (SLP) positions as well as their modifications.

Lack of complete oral feeding often causes delayed discharge of newborn infants from hospital, which may increase the risk of nosocomial patients' infections as well as increasing the cost of hospitalization. Reduction of the factors that adversely affect the introduction of full, effective and safe oral feeding is a very important element of neonatal care. Unfavourable factors such as: saturation decrease, bradycardia or choking episodes are the causes or symptoms of the newborn's stress which may also add to the stress in parents participating in the feeding process. Stress has an obvious detrimental effect on the development of immature brain, causing neuronal atrophy and changes in the hippocampus functioning as well as affecting the immune and neuroendocrine systems. Stress negatively affects mother's lactation due to stress inhibitive effect on the secretion of hormones responsible for milk production. Safe introduction of oral feeding is one of stress-reducing factors for parents. Increased sense of safety

and comfort, in turn, encourages parents of prematurely born infants to try baby feeding on their own.

## PURPOSE

The aim of the study is to compare the advantages of SEP and SLP positioning during bottle-feeding of preterm infants  $\leq 34$  weeks gestational age.

## METHOD

The study will include forty two neonates ( $n=42$ ) born  $\leq 34$  weeks of gestational age. Four bottle-feeding sessions will be tested in each of the newborn: two in the SEP and two in the SLP. The position for the first study will be randomly assigned, then positioning will be changed after each feeding session. In one day, only two consecutive feeding sessions which will be included to the study in order to minimize fatigability as a disrupting factor. The levels of saturation ( $SpO_2$ ) and heart rate (HR) will be measured as the parameters indicative of the newborn's physiological stability. The factors determining the qualitative aspects of feeding included the total time of declines of  $SpO_2 \leq 85\%$ , level of the newborn's alertness according to the Neonatal Behavioral Assessment Scale (NBAS), and the occurrence of choking episodes. The proportion of milk consumed (volume of milk eaten relative to the expected volume) and the duration of the feeding and feeding session will be also recorded.

Each feeding session will be recorded with a video camera. It should be mentioned that participation in the study will not oblige the parents to use any of the positions which will be used during the study and to bottle-feeding. Bottle-feeding will be continued with attempts of the breastfeeding, if only it will be possible.

## INCLUSION CRITERIA

- circulatory and respiratory stability;
- readiness for oral feeding according to each child's Speech-Language Pathologist assessment;
- prematurely born infants who were in the process of being transferred from enteral nutrition (or enteral nutrition + parenteral nutrition) to full

- oral feeding and were fed orally at least 4- 6 times within twenty-four hours;
- parents gave informed consent to participate their infant in the study.

## EXCLUSION CRITERIA

- disorders which could significantly affect the feeding course, such as cleft lip and/or palate, facial paralysis and/or congenital defects of the facial skeleton;
- the presence of detected congenital abnormalities and metabolic diseases; low Apgar score (less than 5 points at the 5th and 10th minute of the measurement);
- administered analgesics, anticonvulsants and sedatives;
- <72 hours from extubation prior the trial;
- parents refusal to participate in the study or when bottle-feeding was not the parental preference.

## DETAILS OF POSITIONING IN SLP AND SEP POSITIONS

SLP: Infant placed in a SLP on the researcher's lap. Head of the infant symmetrically placed between the shoulders, supported by the researcher's. Shoulder girdle higher than pelvic girdle, head and back in a straight line – a slight natural bent of the body is allowed. Legs bend at an angle of approx. 90° in the natural flexion of the knee and ankle joint. The infant's arms close to the midline (on the bottle of researcher's hands).

SEP: Infant placed in a SLP on the researcher's lap. The head rests on the researcher's hand. Shoulder girdle higher than pelvic girdle, head and back in a straight line at an angle of 40-45° to the ground – a slight natural bend of the body is allowed. Legs bend at an angle of approx. 90° in the natural flexion of the knee and ankle joint. The infant's arms close to the midline (on the bottle of researcher's hands).

The research is approved by the Bioethical Commission of the Polish Mother's Memorial Hospital Research Institute, Łódź, Poland - opinion no. 95/2016.

## STUDY DESIGN

The study is designed as a crossover study - alternate study. It will be a randomized trial. Each infant will be bottle-fed four times: twice in the SEP and twice in the SLP. In each of the study positions 84 feeding sessions will be analyzed (total amount of feeding sessions which will be analyzed will be 168). The position for the first trial will be randomly assigned (random table), then positioning will be changed after each feeding session. The study will include observation of the newborn before, during and after the feeding and the following measurements:

- A. 2 minutes before the feeding session: oxygen saturation ( $SpO_2$ ) level, heart rate (HR) (pulse oximeter data), alertness level
- B. 3rd minute of the feeding session:  $SpO_2$ , HR, alertness level
- C. 10th minute of the feeding session:  $SpO_2$ , HR, alertness level, volume of food eaten
- D. the end of the feeding session:  $SpO_2$ , HR, alertness level, volume of food eaten
- E. 10 minutes after the feeding session:  $SpO_2$ , HR, alertness level

The declines of  $SpO_2 \leq 85\%$  level, total time of feeding and feeding session, occurrence chocking episodes also will be recorded.

During the study feeding, normal feeding session procedures will be applied: avoidance of excessive stimuli by ensuring calm environment with limited level of light and noise, pauses in the feeding after a series of suckling (interval feeding), manual support within the articulation apparatus to improve lip tightness and/or mandibular function. Stimulation of the suction reflex will be also allowed.

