# Statistical Analysis Plan

In order to verify hypothesis stated in this research, statistical analysis will be conducted using IBM SPSS v. 25 and Jamovi v1.2.8. Frequency distribution analysis, basic descriptive statistics with Shapiro-Wilk's test for normality of distributions, *t*-tests for independent samples, two-way independent mixed ANOVAs as well as chi-squared tests of independency will be computed.

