## WHAT WILL BE ANALYZED?

- Differences in changes in blood oxygen saturation due to the position of the baby during feeding
- Heart rate variations due to the position of the baby during feeding
- Differences in the change in baby's activity due to the baby's position during feeding
- The position of the baby during feeding and choking episodes
- Differences in the proportion of the volume of eaten food due to the position of the child during feeding
- Differences in feeding times and feeding sessions due to the position of the baby during feeding
- Differences in the time of saturation decrease to the level of  $\leq 85\%$  due to the position of the child during feeding

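### Cheap improvement: state a balanced split of the two alternating sequences and adjust for study-feed order, so that chance imbalance cannot carry a first-versus-second-feed difference into the position comparison

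*Combined protocol and SAP*

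**What the plan says.** STUDY DESIGN describes the trial in these terms: "The study is designed as a crossover study - alternate study". On amounts it says "Each infant will be bottle-fed four times: twice in the SEP and twice in the SLP", and on allocation "The position for the first trial will be randomly assigned (random table), then positioning will be changed after each feeding session". METHOD gives the same allocation rule, sets the size ("The study will include forty two neonates") and limits study feeds per day: "In one day, only two consecutive feeding sessions which will be included to the study in order to minimize fatigability as a disrupting factor".

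Only two sequences are therefore possible: SEP-SLP-SEP-SLP and SLP-SEP-SLP-SEP. Neither section gives an allocation ratio, blocking, or a target number of infants per sequence. The 84 sessions per position in STUDY DESIGN balance the positions, and they do so at any split of the sequences.

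The Statistical Analysis Plan names independent-samples t-tests and then "two-way independent mixed ANOVAs as well as chi-squared tests of independency will be computed". It does not list the ANOVA factors and mentions no order, period or sequence term. Every item under WHAT WILL BE ANALYZED? is a comparison by position, for example "Differences in the proportion of the volume of eaten food due to the position of the child during feeding".

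**The concern.** Read as two study feeds on each of two days, strict alternation gives one position the first study feed of both days and the other position the second. Within an infant, position and study-feed order cannot be told apart. Only the comparison across the two sequences separates them, as in any two-sequence crossover. If the sequences are unequal in number and the two feeds of a day differ, part of that difference enters the position estimate, and no named analysis is stated to remove it.

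The contrast at issue is first versus second study feed, not first versus second feed of the day. Eligible infants "were fed orally at least 4- 6 times within twenty-four hours", so other feeds may come before either study feed. METHOD gives fatigability as the reason for the daily limit, which makes an order difference a fair question but does not show that one exists.

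The pre-feed readings of SpO2, heart rate and alertness partly cover those three outcomes. Proportion eaten, feeding times, choking and time at SpO2 ≤85% have no pre-feed value. At stake is an avoidable shift in the point estimate and, in a paired analysis, some lost precision.

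**Working it through.** **Plan's own figures.** 42 × 4 = 168 sessions and 42 × 2 = 84 per position, as STUDY DESIGN states. The documents give no power calculation, SD or effect size to reproduce.

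**Inputs.** From the documents: N = 42, four sessions per infant, two alternating sequences. Assumed: simple 1:1 randomisation; total session SD of 1 before any order effect; order difference delta of 0.2 to 0.5 SD; within-infant correlation rho of 0.1 to 0.5; no position effect.

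**1. Shift.** Let n1 infants start in SEP and n2 in SLP. In the first group SLP falls on the second study feed, so SLP − SEP gains delta. In the second group it loses delta. Averaged over infants, the shift is delta × (n1 − n2)/42. A pure day-to-day change cancels at any split, because both positions occur on each day.

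**2. How unequal the split might be.** Binomial(42, 0.5):

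| Split | Probability | Shift |
|---|---|---|
| 21:21 exactly | 0.12 | 0 |
| 25:17 or worse | 0.28 | 8/42 = 0.19 × delta at 25:17 |
| 26:16 or worse | 0.16 | 10/42 = 0.24 × delta at 26:16 |
| 27:15 or worse | 0.09 | 12/42 = 0.29 × delta at 27:15 |

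The mean of |n1 − n2|/42 is 0.12. The mean of (n1 − n2)/42 is zero. At 25:17 the shift is 0.04 SD for delta 0.2 and 0.10 SD for delta 0.5.

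**3. Paired analysis without an order term.** The within-infant difference between two-feed means has variance (1 − rho)(1/2 + 1/2) = 1 − rho. Random sequence adds ±delta, hence delta². The relative increase is delta²/(1 − rho): 0.04/0.7 = 6% and 0.04/0.5 = 8% at delta 0.2; 0.25/0.7 = 36% and 0.25/0.5 = 50% at delta 0.5.

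**4. The named independent t-test at 25:17, delta 0.5.** The true standard error of the position difference is √((1 − rho)/42). The test's critical difference is about 1.974 × √[(2/84)(1 + (0.25/4)(1 − 0.19²))] = 0.314. The shift is 0.095. The normal approximation to the two-sided rejection rate, P(Z > (0.314 − 0.095)/SE) + P(Z > (0.314 + 0.095)/SE), is set beside simulation:

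| rho | SE | Approximation | Simulation |
|---|---|---|---|
| 0.1 | 0.146 | 7.0% | 7.2% to 7.3% |
| 0.2 | 0.138 | 5.8% | 5.9% to 6.3% |
| 0.3 | 0.129 | 4.6% | 4.7% to 4.9% |
| 0.5 | 0.109 | 2.3% | 2.5% to 2.7% |

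Type I error at this split is therefore below 5% only if rho is about 0.3 or more. Averaged over simple randomisation, it is 2.3% / 0.9% at delta 0.2 and 3.9% / 2.2% at delta 0.5 (rho 0.3 / 0.5).

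**5. After the change.** At 21:21 the shift is zero. With an order term it is zero at any split, at a variance ratio of 42²/(4 × n1 × n2): 1.000 at 21:21 and 1764/(4 × 25 × 17) = 1.038 at 25:17. In simulation of an infant-level analysis at 25:17 with delta 0.5, the order term takes the mean shift from 0.095 to 0.00, and type I error from 6.2% / 6.6% to 5.1% / 5.0% (rho 0.3 / 0.5).

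**The case against.** The strongest reply is that nothing here is shown to be wrong. The starting position is random, so the comparison is unbiased over repeated randomisations. Delta is undocumented. The daily limit on study feeds is itself a safeguard against fatigue. A random table may well have been used with blocks, and a mixed ANOVA whose factors are not listed might include order. The size is also small: at delta 0.2 the average absolute shift is 0.122 × 0.2 = 0.024 SD, about a fifth of the paired standard error (0.129 at rho 0.3, 0.109 at rho 0.5).

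Most of this stands, and it sets the weight of the point. It rules out two readings that a reader might infer. One is that alternation biases the comparison or makes it uninterpretable. It does not, because the two sequences together separate position from order. The other is that an unequal split will shift the result. The documents do not report a split, exclude blocking or show that the two feeds differ, so a shift is possible but not established.

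The reply does not remove the gap. Unbiasedness in expectation does not protect the one trial that is run. A reader cannot tell whether the sequences were balanced or order was modelled. Independent t-tests and chi-squared tests of position carry no order term. Nor can the low type I error of the t-test be taken as general reassurance: it comes from ignoring the pairing, and at 25:17 with delta 0.5 it fails when rho is 0.2 or lower.

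A further fair objection is that the remedy is more than one added term, because the named tests cannot carry it. That is accepted and counted in the cost.

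**Conclusion.** The point holds as a low-cost improvement, not as a flaw that undermines the trial. Sequence balance and an order term are both unstated. If the second study feed differs from the first, an unequal split moves the SLP − SEP difference by delta × (n1 − n2)/42: on average 12% of delta in absolute terms, 19% at 25:17, with expectation zero. If delta is zero there is no effect.

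The probabilities rest on simple 1:1 randomisation, which the documents neither state nor exclude. The 6% to 8% variance increase rests on delta 0.2 SD, rho 0.3 to 0.5 and a paired analysis, which the plan does not name. For the independent t-test that it does name, at 25:17 and delta 0.5 SD, type I error is under 5% only from rho of about 0.3 upward, and about 6% to 7% at rho 0.1 to 0.2. Neither a general inflation of type I error nor a general assurance that it stays below 5% is supported.

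**What to change.** **METHOD and STUDY DESIGN.** State that infants are randomised 1:1 to SEP-first or SLP-first in permuted blocks of varying size, giving 21 infants per sequence, with position alternating after each session as now. Six blocks of 4 and three blocks of 6, in random order, would make up 42; other arrangements serve equally well. Report the achieved split.

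**Statistical Analysis Plan.** Analyse position with study-feed order within the day (first/second) as a fixed effect, in a model that accounts for repeated sessions within infant. If choking is too rare to support that model, say that the 21:21 balance is relied on for that outcome.

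**Cost.** A blocked list, and replacement of the independent t-tests and chi-squared tests by within-infant models that can carry the order term. The term itself adds no variance at 21:21 and 3.8% at 25:17. The number of infants, sessions and days and the alternation are unchanged. The two parts overlap: at 21:21 the term does not change the point estimate, and with the term exact balance is not essential. Stating both covers withdrawals and outcomes too sparse to model.

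### The plan has no rule for sessions that end before minute 10; if the minute-10 reading is a level of the mixed ANOVA, those sessions drop out and the position comparison is conditioned on session length.

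*Combined protocol and SAP*

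**What the plan says.** STUDY DESIGN in the protocol schedules SpO2, heart rate and alertness at five points: A (2 minutes before), B (minute 3), C ("10th minute of the feeding session"), D ("the end of the feeding session") and E (10 minutes after). The volume eaten is recorded at C and D. C is tied to the clock; D and E are tied to when the session stops. No minimum, maximum or expected session length is given, and nothing says what to record at C if the session is already over.

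The same section fixes the number of sessions. Every infant contributes four feeds, two per position, which gives 84 sessions for SEP and 84 for SLP. For the trial as a whole, the protocol states: "total amount of feeding sessions which will be analyzed will be 168".

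The only repeated-measures method named in the Statistical Analysis Plan is "two-way independent mixed ANOVAs". The SAP does not name the factors, the time levels or the unit that forms a row, and it has no missing-data rule. Its list of analyses (WHAT WILL BE ANALYZED?) covers changes in saturation and in activity and variations in heart rate by position. It also includes "Differences in feeding times and feeding sessions due to the position of the baby during feeding".

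**The concern.** A session that ends at, say, minute 7 has valid A, B, D and E readings but no in-session C, because D comes before minute 10. C is then not a lost measurement; it does not exist. A classical mixed ANOVA with position as one factor and time A to E as the other needs a complete row. If C is a level of the time factor, the whole session goes, including its four valid readings.

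Two things would follow. First, fewer than 168 sessions would be analysed. Second, whether a session counts would depend on its length, which is observed after randomisation and which the plan treats as something position may change. If one position produces more short sessions, the two positions would be compared on differently selected feeds. That could create or hide a difference in three of the seven listed analyses: saturation, heart rate and activity.

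**Working it through.** **1. The plan's own figure.** "The study will include forty two neonates" with four sessions each: 42 × 4 = 168 in total and 42 × 2 = 84 per position. Both stated counts reproduce.

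**2. Sessions kept if C is required.** Let f be the share of sessions that end before minute 10. The documents do not give f, so it is varied. Sessions kept = 168 × (1 − f). The detectable difference in SD units is (1.960 + 0.842) × √(2 / [84 × (1 − f)]). It assumes two-sided 5% alpha, 80% power and independent sessions, none of which the plan states. If the infant rather than the session forms the row, infants kept = 42 × (1 − f)⁴, assuming independent sessions.

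| f | Sessions kept | Detectable difference (SD) | Infants with all four sessions complete |
|---|---|---|---|
| 0% | 168 | 0.43 | 42 |
| 5% | 160 | 0.44 | 34 |
| 10% | 151 | 0.46 | 28 |
| 20% | 134 | 0.48 | 17 |
| 30% | 118 | 0.52 | 10 |
| 50% | 84 | 0.61 | 3 |

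With the session as the row, the loss of precision is modest unless f is large.

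**3. Selection, for a level.** Assumptions: session length is lognormal with log-SD 0.4; SpO2 has SD 3 points and correlation r of 0.3 or 0.5 with log length within position; position has no true effect on SpO2. For median m, let c = ln(10/m)/0.4. The share lost is Φ(c), and the mean standardised log length among kept sessions is λ = φ(c)/(1 − Φ(c)). The false difference is 3 × r × (λ₂ − λ₁).

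- m = 15: c = −1.014, lost 15.5%, λ = 0.283.
- m = 12: c = −0.456, lost 32.4%, λ = 0.532.
- m = 10: c = 0, lost 50%, λ = 0.798.
- m = 20: c = −1.733, lost 4.2%, λ = 0.093.
- m = 14: c = −0.841, lost 20.0%, λ = 0.350.

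| Medians (min) | Lost | λ₂ − λ₁ | r = 0.3 | r = 0.5 |
|---|---|---|---|---|
| 15 / 15 | 15.5% / 15.5% | 0 | 0 | 0 |
| 15 / 12 | 15.5% / 32.4% | 0.250 | 0.22 | 0.37 |
| 20 / 14 | 4.2% / 20.0% | 0.257 | 0.23 | 0.39 |
| 15 / 10 | 15.5% / 50% | 0.515 | 0.46 | 0.77 |

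The last two columns are SpO2 points in absolute value. At 15 / 12, about 84 × 0.845 = 71 and 84 × 0.676 = 57 sessions are kept.

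**4. Selection, for a change.** The SAP targets changes. For the change from A to D, with equal SDs at both points, the false difference is 3 × (r_D − r_A) × (λ₂ − λ₁), where r_A and r_D are the correlations of length with SpO2 at A and at D. If r_A = r_D it is 0 in every row of the table. If r_A = 0, the values for levels return. The documents say nothing about either correlation.

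**The case against.** A reader might infer that the plan as written throws short sessions away and that the comparisons are confined to slower feeds. The documents do not support this as fact. The SAP never says that C is a required level, and the only stated intention is to analyse all 168 sessions. Dropping sessions is an inference from how a classical mixed ANOVA works.

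Nor is there evidence that short sessions will occur. The protocol allows pauses during feeding and times the feeding and the session separately without defining either. C is tied to the session, so a short feed with pauses may still run past minute 10.

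A reader might also take 0.2 to 0.8 SpO2 points as the expected bias. That range describes a level under assumed inputs. The planned target is change, for which the bias can be zero, and it is also zero when short sessions are equally common in both positions.

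All of this stands, and it is why the point is conditional. What it does not remove is the gap itself: a clock-based reading sits before an event-based one, session length is an outcome, and no rule connects them. The intention to analyse 168 sessions makes such a rule more necessary, because the named method cannot keep sessions with an incomplete row.

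**Conclusion.** The point holds conditionally. A session that ends before minute 10 has no in-session C. If C is a level of the mixed ANOVA, that session is lost with its other four readings, fewer than 168 sessions are analysed, and the position comparison is conditioned on session length. This rests on two things that the documents leave open: that C is a time level, which is the natural reading of a position-by-time analysis, and that some sessions are shorter than 10 minutes.

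Bias in the position contrast needs two further conditions: unequal shares of short sessions, and a link between session length and the change in the outcome. Its size is therefore unknown. It runs from nothing (all sessions reach minute 10, equal shares, or length related equally to baseline and later readings) to about 0.8 SpO2 points under the most unfavourable of the assumed inputs. The change is worth making because it costs little and the rule should be fixed before the data are seen.

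**What to change.** In the SAP, replace the mixed ANOVA for SpO2, heart rate and alertness with a linear mixed model. Its fixed effects are position, time point and position × time, with random effects for infant and for session within infant. Fit it to A, B, D and E from all 168 sessions, that is 168 × 4 = 672 scheduled readings per outcome.

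Keep C out of that model. Report it descriptively for sessions still in progress at minute 10, with their number by position. For the volume eaten at minute 10, use the final volume when the session ended earlier.

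The cost is SAP wording; no new data are needed. There are two downsides. Minute 10 becomes a conditional, descriptive time point. D and E are available for short sessions too, but they still fall at clock times set by session length, so a difference at D or E may partly reflect when the reading was taken. The report should say so.
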